Day 2, 4 and 6: 0 hours (immediately before AM dose);
Day 7: 0, 1, 2, 4, 6, 9, 10, 11, 12, 14, and 16 hours post AM dose. The collections at 0 and 10 hours are immediately before the AM and PM doses, respectively;
Day 8: 0 hours (corresponding to 24 hours after AM dose on Day 7) and 10 hours (corresponding to 24 hours after PM dose on Day 7);
Day 9: 48 hours after PM dose on Day 7;
Day 11: 96 hours after PM dose on Day 7.
- ¹⁴ Urine will be collected for determination of spot urine osmolality and urine specific gravity at the following timepoints:
Day -1: 0 (start), 1, 2, 4, 6, 9, 10, 11, 12, and 14 hours.

Day 1: 0, 1, 2, 4, 6, 9, 10, 11, 12, and 14 hours post AM dose. The collections at 0 and 10 hours are immediately before the AM and PM doses, respectively;

Day 2: 0 hours (immediately before AM dose on Day 2, corresponding to 24 hours after AM dose on Day 1).

Day 7: 0, 1, 2, 4, 6, 9, 10, 11, 12, and 14 hours post AM dose. The collections at 0 and 10 hours are immediately before the AM and PM doses, respectively;

Day 8: 0 hours (corresponding to 24 hours after AM dose on Day 7).

Note: Subject may not be able to void at all timepoints - see [Section 6.1.7](#). For all voids, the volume (mL) and the date and time of void will be recorded.

- ¹⁵ Record daily urine output on Day -1, Day 1 and Day 7. On Day -1, measurement will begin 24 hours before the expected time of first study medication on Day 1 AM. On Day 1 and Day 7, measurements will begin immediately before the AM dose and will continue for 24 hours into the morning of Day 2 and Day 8, respectively.
- ¹⁶ Blood samples for determination of plasma copeptin will be taken at approximately the same time of day (in the morning and, on dosing days, before the lixivaptan dose).
- ¹⁷ Subjects will be admitted to the CRU in the evening of Day -2 or in the morning of Day -1. For subjects admitted to the CRU on Day -2, the Screening period will be until Day -3. For subjects admitted to the CRU on Day -1, the Screening period will be until Day -2.

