The number and percentage of subjects who show uninterrupted suppression of urine osmolality over 24 hours, defined as spot urine osmolality <300 mOsm/kg at each time point during a 24-hour measurement period, as well as over 14 hours following the PM dose, will be determined for Day -1, Day 1, and Day 7 by dose and by cohort. The above summary will additionally be presented similarly for subjects who show uninterrupted urine osmolality ≤250 mOsm/kg over 24 hours or 14 hours (PM). The 24-hour measurement periods will be calculated as follows:

- For Day -1, from time = 0 on Day -1 until time = 0 (AM predose) on Day 1;
- For Day 1, from time = 1 h on Day 1 until time = 0 (AM predose) on Day 2; and
- For Day 7, from time = 1 h on Day 7 until time = 0 on Day 8

PK/PD STATISTICAL ANALYSIS PLAN Document:

Author: [name] Version Number: 1.0 Version Date: 12 Aug 2019

Template No: CS\_TP\_BS016 - Revision 5 Reference: CS\_WI\_BS005

Effective Date: 01Apr2018

Palladio BiosciencesInsert Customer Name/Logo PK/PD STATISTICAL ANALYSIS PLAN: PROTOCOL PA-102 Page 35 of 39

In addition, the number and percentage of subjects with spot urine osmolality <300 mOsm/kg at each time point during the three 24-hour measurement periods (Day -1, Day 1, and Day 7) will be determined by dose and by cohort. The above summary will additionally be presented similarly for subjects who with spot urine osmolality ≤250 mOsm/kg at each time point.

Figure(s) of mean (±SD) urine osmolality versus time by Day (overlaid within plot), cohort, and CKD stage within cohort, will be produced. Figure(s) of mean (±SD) PD endpoint versus Day by cohort and CKD stage within cohort will be produced for urine output, fluid intake, fluid balance, TKV, LV, and plasma copeptin. All the above PD figures will use a linear scale for the PD dependent variable, using the observed values.

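### The 24-hour osmolality suppression rule demands 11 passing samples on Day -1 but 10 on Days 1 and 7, which can only lower the off-drug count

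*SAP*

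**What the plan says.** PK/PD SAP 15.1 tabulates, by dose and by cohort, how many subjects have uninterrupted suppression of urine osmolality on Day -1, Day 1 and Day 7. Suppression is "defined as spot urine osmolality <300 mOsm/kg at each time point during a 24-hour measurement period", with a parallel summary at ≤250 mOsm/kg. The three windows are:

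- Off drug, starting with the 0 h sample: "For Day -1, from time = 0 on Day -1 until time = 0 (AM predose) on Day 1"
- On the first dosing day, leaving out the predose sample: "For Day 1, from time = 1 h on Day 1 until time = 0 (AM predose) on Day 2"
- On the last dosing day, with the same pattern: "For Day 7, from time = 1 h on Day 7 until time = 0 on Day 8"

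The collection times are in Protocol 12.2, Table 12-1, footnote 14:

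- Off drug: "Day -1: 0 (start), 1, 2, 4, 6, 9, 10, 11, 12, and 14 hours"
- First dosing day, with the same nominal times: "Day 1: 0, 1, 2, 4, 6, 9, 10, 11, 12, and 14 hours post AM dose"
- Last dosing day, again the same: "Day 7: 0, 1, 2, 4, 6, 9, 10, 11, 12, and 14 hours post AM dose"

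A 0 h sample on the following morning closes each window. For Day -1 this is the Day 1 predose sample. For Day 1 it is "Day 2: 0 hours (immediately before AM dose on Day 2, corresponding to 24 hours after AM dose on Day 1". For Day 7 it is the 0 h sample on Day 8. Neither document states the number of samples per window or gives a reason for the different start times.

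**The concern.** Under an all-samples-must-pass rule, the number of samples is part of the definition of a responder. Here the off-drug day has one more hurdle than the on-drug days. The trial has no placebo arm, so Day -1 is the only off-drug reference for this count. A reader of the table will set Day 1 and Day 7 beside Day -1, and any effect of the extra sample on that contrast favours the drug.

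The mismatch also departs from the time-matching that the plan uses elsewhere. For change from baseline, SAP 15.1 and Protocol 7.7.2 pair each post-dose time with the same time on Day -1, except that the AM predose assessment takes its baseline from Day 1. That Day 1 predose sample already closes the Day -1 window. The Day -1 0 h sample is therefore not the baseline for any time point, yet it can by itself disqualify a subject from the off-drug count.

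Characterizing osmolality over 24 hours is a secondary objective, and Protocol 1.4 treats reduction below 300 mOsm/kg as predictive of efficacy, so the count will be looked at. In a cohort of 8, one reclassified subject moves the rate by 1/8 = 12.5 percentage points.

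**Working it through.** The plan states no figure to reproduce, so the check is a count followed by a sizing exercise.

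**Count.** Scheduled times from footnote 14, placed in the SAP 15.1 windows, with the closing next-morning sample labelled 24 h:

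| Window | Samples (h) | Number | First to last |
|---|---|---|---|
| Day -1 | 0, 1, 2, 4, 6, 9, 10, 11, 12, 14, 24 | 11 | 24 h |
| Day 1 | 1, 2, 4, 6, 9, 10, 11, 12, 14, 24 | 10 | 23 h |
| Day 7 | 1, 2, 4, 6, 9, 10, 11, 12, 14, 24 | 10 | 23 h |

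The only difference is the Day -1 0 h sample. After the PM dosing time the samples are 11, 12, 14 and 24 h on all three days, so the 14-hour summary is unaffected.

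**Direction.** P(all 11 pass) = P(the same 10 pass) × P(0 h passes, given the 10 pass). The last factor is at most 1, so the extra sample cannot raise the Day -1 count. This holds whatever the osmolality pattern over the day.

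**Size, independent samples.** The documents give no off-drug pass rates, so these values are assumed. With a common pass probability p, the fall in the Day -1 rate is p^10 − p^11:

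| p | 10 samples | 11 samples | Fall | Subjects of 8 |
|---|---|---|---|---|
| 0.5 | 0.0010 | 0.0005 | 0.0005 | 0.004 |
| 0.8 | 0.1074 | 0.0859 | 0.0215 | 0.17 |
| 0.9 | 0.3487 | 0.3138 | 0.0349 | 0.28 |
| 0.99 | 0.9044 | 0.8953 | 0.0090 | 0.07 |

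Setting the derivative 10p^9 − 11p^10 to zero gives p = 10/11. The maximum fall is 0.3855 − 0.3505 = 0.035, or 0.28 of 8 subjects and 1.1 of 32.

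**Size, correlated samples.** This is a simulation with 500,000 subjects per scenario. Each subject has an exchangeable latent normal with correlation ρ. The nine samples from 1 to 14 h share a daytime pass probability, and the 0 h and 24 h samples share a morning one. All values are assumed. Entries are the fall in the Day -1 rate:

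| Daytime / morning pass probability | ρ = 0.3 | ρ = 0.6 | ρ = 0.8 |
|---|---|---|---|
| 0.5 / 0.3 | 0.0088 | 0.0198 | 0.0273 |
| 0.7 / 0.5 | 0.0275 | 0.0361 | 0.0394 |
| 0.9 / 0.5 | 0.1072 | 0.1063 | 0.0934 |
| 0.95 / 0.7 | 0.1097 | 0.0939 | 0.0783 |
| 0.9 / 0.9 | 0.0221 | 0.0132 | 0.0072 |

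The range is 0.0072 to 0.1097, which is 8 × 0.0072 = 0.06 to 8 × 0.1097 = 0.88 subjects per cohort. The largest falls need morning samples that are much harder to pass than daytime ones.

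**After the change.** Starting Day -1 at 1 h leaves 1, 2, 4, 6, 9, 10, 11, 12, 14 and 24 h: 10 samples at the same nominal times on all three days.

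**The case against.** The best defence is that the Day -1 window is the only one that spans a literal 24 hours. Day 1 has to drop 0 h because that sample is predose, and nothing forces the same on Day -1. The first part is true, and it shows that the Day 1 window is sound. It does not make the three counts comparable as tabulated.

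A second defence is that nothing is hidden. The same SAP section tabulates pass counts at each time point and lists all PD data by subject, so a matched 10-sample count can be recovered. That is also true. However, the per-time-point table does not show whether the 0 h sample alone disqualified a subject, and a reader should not need the listings to repair the summary.

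A third objection concerns weight, and it stands. The count is descriptive, and SAP 15.1 attaches no difference, interval or test to it. A reader might infer that the trial's main osmolality result is compromised. The documents do not give it that rank: Protocol 2.2.2 names spot urine osmolality and 24-hour urine output, and the SAP also plans time-matched changes, mean profiles and per-time-point counts.

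A reader might also infer a large bias on the ground that morning urine is concentrated. The documents do not say this of these samples. Protocol 6.1.7 has subjects empty the bladder completely 15 minutes before each collection, so the specimen is newly formed urine. Protocol 1.2 describes urine concentration defects as ADPKD progresses. A subject who has passed the other ten samples has also already passed one morning sample. Reduced concentrating ability in CKD3 cuts both ways: more subjects might be suppressed off drug, but the extra sample would be easier to pass.

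Finally, subjects admitted on the morning of Day -1 might lack a 0 h sample. SAP 7.3 leaves missing data as missing, and the SAP does not say how a missing sample counts under the rule. If it is ignored, those subjects are judged on the same 10 samples. This is an ambiguity and not evidence of further bias.

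**Conclusion.** The point holds as a one-directional mismatch of probably small size. The 11, 10 and 10 sample counts follow directly from the two documents, and the direction follows from the rule itself, with no assumption about physiology.

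The size does rest on assumptions. It is near zero if few untreated subjects are below threshold throughout. It is at most 0.035 with independent, equally likely samples, and about 0.01 to 0.11 in the correlated scenarios, always under one subject of 8.

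A claim that a large fraction of baseline responders is lost would need conditional pass rates that the documents do not contain. It could also mislead: at p = 0.5 with independent samples the relative loss is 50%, but the absolute loss is 0.0005.

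**What to change.** In PK/PD SAP 15.1, define the Day -1 period as running from 1 h on Day -1 to the AM predose sample on Day 1, for both the <300 and the ≤250 mOsm/kg summaries. All three days then use the same 10 nominal times. The per-time-point table is built on the same three windows, so add a clause that keeps the Day -1 0 h value there.

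The cost is one SAP line and at most a trivial programming change, with no new data. The downside is that the Day -1 samples then span 23 h instead of 24 h, as they already do on Days 1 and 7.

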### 15.2. PHARMACOKINETIC-PHARMACODYNAMIC RELATIONSHIPS

Figures of individual/mean observed and/or change from baseline PD variables versus individual/mean PK endpoint(s) (lixivaptan only) will be produced for urine osmolality, urine output, TKV, LV, plasma copeptin, and eGFR, based on overlapping subjects/data in the PK analysis set and PD analysis set (excluding subjects/data affected by protocol deviations/events). Plot(s) for urine osmolality will use PK concentrations at all nominal time points coinciding with urine osmolality. Plot(s) for plasma copeptin and eGFR will plot Day 2 PD versus Day 1 PK parameter AUC(0-inf) or AUC(0-last), depending on appropriateness. An additional plot will show Day 2 plasma copeptin versus Day 1 PK parameter Cmax. Plot(s) for urine output will plot Day 1 PD versus Day 1 PK parameter AUC(0-inf) or AUC(0-last), depending on appropriateness. Plot(s) for eGFR will plot Day 8 PD versus Day 7 PK parameter AUC(0-14). Plot(s) for urine output, TKV, LV, and plasma copeptin will plot Day 7 PD versus Day 7 PK parameter AUC(0-14). An additional plot will show Day 7 plasma copeptin versus Day 7 PK parameter Cmax. Plot(s) will use PK parameters for Day 1 AM or Day 7 PM. All PD versus PK

PK/PD STATISTICAL ANALYSIS PLAN Document:

Author: [name] Version Number: 1.0 Version Date: 12 Aug 2019

Template No: CS\_TP\_BS016 - Revision 5 Reference: CS\_WI\_BS005

Effective Date: 01Apr2018

Palladio BiosciencesInsert Customer Name/ Logo PK/PD STATISTICAL ANALYSIS PLAN: PROTOCOL PA-102 Page 36 of 39

figures will use a linear scale for the PD dependent variable.

# **16.** SAFETY OUTCOMES

See Non-PK/PD SAP.

# 17. DATA NOT SUMMARIZED OR PRESENTED

See Non-PK/PD SAP.

Document: PK/PD STATISTICAL ANALYSIS PLAN

Author: [name] Version Number: 1.0
Version Date: 12 Aug 2019

Template No: CS\_TP\_BS016 – Revision 5 Reference: CS\_WI\_BS005

Effective Date: 01Apr2018

Palladio BiosciencesInsert Customer Name/ Logo PK/PD STATISTICAL ANALYSIS PLAN: PROTOCOL PA-102 Page 37 of 39

# **APPENDIX 1. Programming Conventions for Outputs**

### **OUTPUT CONVENTIONS**

Outputs will be presented according to the IQVIA Global Biostatistics Standard Output Conventions, which is available upon request.

### **DATES & TIMES**

Depending on data available, dates and times will take the format dd-mmm-yyyy; times will take the format hh:mm:ss; combined dates and times will take the format dd-mmm-yyyyThh:mm:ss.

### **SPELLING FORMAT**

English US.

### PRESENTATION OF TREATMENT GROUPS

For outputs, treatment groups will be represented as follows and in that order:

Treatment group	Treatment label	
CKD1/2 200 mg	Cohort 1	
CKD3 200 mg	Cohort 2	
CKD1/2 50 mg	Cohort 3	

Document: PK/PD STATISTICAL ANALYSIS PLAN

Author: [name] Version Number: 1.0

Version Date: 12 Aug 2019

Template No: CS\_TP\_BS016 - Revision 5 Reference: CS\_WI\_BS005

Effective Date: 01Apr2018

Palladio BiosciencesInsert Customer Name/ Logo PK/PD STATISTICAL ANALYSIS PLAN: PROTOCOL PA-102 Page 39 of 39

Treatment group	Treatment label
Treatment group	Treatment laber
	-
CKD3 50 mg	Cohort 4
Not allocated to a	Not allocated
cohort	

# APPENDIX 2. Partial Date Conventions

The only items that may have partial dates are medical history start/end dates, CKD initial diagnosis date and AE start/end dates. All other dates collected in the study should be a complete date with dd-mmm-yyyy format.

Document: PK/PD STATISTICAL ANALYSIS PLAN Author: [name]

Author: [name] Version Number: 1.0

Version Date: 12 Aug 2019

Template No: CS\_TP\_BS016 – Revision 5 Reference: CS\_WI\_BS005

Effective Date: 01Apr2018

Biostatistics File Note

Page 1 of 1

### 1.0 INSTRUCTIONS

1.1 Use this form to document project specific file notes to be made part of the permanent study file. This may include some type of process deviation or simply an explanatory note. If the form is used to document process deviations which impact on other functions, ensure that the file note is circulated to those functional groups and the Project Leader.

Form No.: CS\_FM\_BS020 Revision 4

Effective Date: 29Nov2019

Reference: CS\_OP\_BS001

**Biostatistics File Note** 

Page 1 of 2

### Section A

**Customer:** 

Palladio Biosciences

**Project Code:** 

WYA34000

**Protocol Number:** 

PA-102

Title of Note:

Urine Osmolality and Copeptin sample exclusion due to non-drug related

anomaly

